5.6 Outcome measures

5.6.1 **Primary outcome measures**

To assess the feasibility of conducting a full CRT in the future, the primary outcome measures are mainly:

Trial-related outcome measures

- Participants' compliance to and satisfaction with Natrox device
- Recruitment and attrition rates, willingness of patients to be consented and randomised, response rates to questionnaires, and degrees of missing data
- Testing of eligibility criteria and ability/willingness of clinical staff to partake in recruitment of participants
- Ability of sites and clinicians to recruit and randomise patients
- To assess any training requirements
- Adequacy of duration of follow-up (e.g. in relation to foot ulcer healing)
- Fitness for purpose of data collection methods including across and between care settings
- Suitability of inclusion/exclusion criteria and outcome measure tools.
- Adverse events

5.6.2 **Secondary outcome measures**

This study also aims to record wound characteristics and patient-related outcomes measures, as well as safety endpoints and microbiology assessments.

The main clinical outcome for this trial will be the efficacy of the Natrox oxygen therapy in terms of wound healing. For all participants, wound healing will be measured

Foot ulcer size, measured with wound grid tool (week -4, 0, 3, 6, 9, 12). Measured in % change in cm² - between week 0 and weeks, 3, 6, 9, and 12 respectively

Assessment wound size and characteristics (wk 0,3,6,9,12)

- Clinical characterisation of wound (incl. erythema, purulence, odour), wound closure status
- PUSH and, if applicable, SINBAD DFU score

Extended safety outcome measures, general and in relation to applied Natrox (ongoing):

- Wound infection incidence
- Need for secondary interventions (incl. need for surgery, admission to hospital, iv antibiotics)
- (indirect) reaction to Natrox, the web itself or oxygen therapy
- Any other adverse events

Patient-reported outcome measures (wk 0, 6, 12)

- Quality of life score (EQ-5D-5L and Cardiff Wound Impact Questionnaire)

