8.2 Primary outcome statistics

The primary objective for this pilot study is the feasibility of conducting a larger scale randomised controlled trial. The secondary outcome statistics (on efficacy) will aid to inform the success of this pilot study and will therefore inform whether a larger scale trial is indicated. This will be based on signs of clinical effectiveness, positive patient feedback on the intervention, positive changes in foot ulcer related quality of life, recruitment to time and target, low attrition rates, minimal data queries and lack of or low number of adverse events. If the effect size of the Natrox intervention pedal is large enough, then this pilot trial may possibly provide a definitive answer concerning its clinical effectiveness.

The following descriptive statistics will be reported on:

- Number of patients screened
- Number of patients eligible/ineligible, and percentage of patients consented into the trial

Number of patients completed the trial/discontinued (plus reasons if discontinued)

Patient feedback on the use and comfort of the Natrox device, and compliance with the prescribed therapy regime will be summarised in tabular and graph format.

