8.3 Secondary outcome statistics

The clinically-related objective for this trial is the healing rate of the foot ulcers, as assessed by tracing the wound using a Coloplast measuring grid, or an equivalent performance-equal measuring tool.

The average difference between time points and baseline (week 0) will be calculated per group, 12 weeks being the primary endpoint but weeks 3, 6 and 9 will also be analysed. To compare the groups, the Mann-Whitney U-test will be applied (data will be tested for normal distribution and if applicable, t-test will be applied).

The average change in healing at 12 weeks between the Natrox cohort and the control cohort within the study will be compared using the Mann-Whitney U-test or, if data normally distributed, t-test. Application of this analysis will depend on sample size of control cohort.

The average baseline demographics for participants in each group (Natrox and control) will be described and compared to ascertain the distribution of participants' data for: sex, age, HbA1c level, baseline wound size (cm2), PUSH score, SINBAD DFU grading score (if applicable), EQ5-5D-5L score, CWIQ score, duration of wound (weeks), neuropathy status, ischaemia status.

Other clinical parameters will be recorded too, since they are known to be significantly associated with non-healing of foot ulcers: diabetes status, peripheral arterial disease, heart failure, pretibial oedema (Prompers et al, 2008)

The Chi-squared test will be applied to the above cross-tabulation to determine if there is a significant difference in distribution of treatment outcome in terms of 'status wound healed' (Natrox vs control).

To evaluate the wider effects of the Natrox topical oxygen therapy regime on foot ulcer healing, the following parameters will be compared (median difference between week 0 and different follow-up time points):

- PUSH score
- SINBAD grading score
- Visual analogue pain score
- EQ5-5D-5L score
- CWIQ score

To compare, Mann-Whitney U-test between cohorts, since data is ordinal.

The sample size in this feasibility trial is too small to conduct Cox proportional hazards regression analysis to investigate the role of the dressing regime choice and other in wound healing rates.

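### Section 8.3 plans about 19 between-arm significance tests, and nothing confines conclusions on effectiveness to the week-12 ulcer-area comparison that it already marks as leading

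*Protocol*

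**What the plan says.** Efficacy is a secondary objective of this feasibility trial (protocol sections 2 and 4.2). Section 5.6.2 names wound healing, measured as percentage change in cm² from week 0, as the main clinical outcome. Section 6.1 also gives wound healing rates first place among the clinical outcomes.

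Section 8.3 compares ulcer area between arms by Mann-Whitney or t-test, with "12 weeks being the primary endpoint but weeks 3, 6 and 9 will also be analysed". It adds a chi-squared test "to determine if there is a significant difference in distribution of treatment outcome in terms of 'status wound healed' (Natrox vs control". For PUSH, SINBAD, pain, EQ-5D-5L and CWIQ, introduced as wider effects, it says "the following parameters will be compared (median difference between week 0 and different follow-up time points" and gives the method as "To compare, Mann-Whitney U-test between cohorts, since data is ordinal". The section states no significance level and does not call any of these tests exploratory.

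Section 8.2 says that the efficacy statistics will help show whether a larger trial should follow. The basis it gives reads "This will be based on signs of clinical effectiveness, positive patient feedback on the intervention, positive changes in foot ulcer related quality of life", together with recruitment, attrition, data queries and adverse events. It adds that, if the effect is large enough, the pilot might settle the question of clinical effectiveness.

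**The concern.** Unadjusted secondary tests in a pilot are usually harmless because nobody draws a conclusion from them. This protocol leaves room to do so. Section 8.3 uses the language of significance testing over many outcomes and visits. Section 8.2 then gives the efficacy results two uses, as an input to the decision on a larger trial and possibly as a final answer on effectiveness. It does not say which result would serve for either.

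With this many comparisons and 12 patients per arm, one nominal p below 0.05 somewhere is weak evidence. As written, such a result on, say, PUSH at week 6 or CWIQ at week 12 could be reported as a significant benefit and counted as a sign of effectiveness, even if the week-12 area comparison showed nothing.

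**Working it through.** The protocol states no alpha, power or error rate, so there is no figure of its own to reproduce first.

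**Step 1. Count the tests.** Visits come from Table 2, section 5.6.2 ("Assessment wound size and characteristics (wk 0,3,6,9,12") and the protocol summary, which puts the patient-reported outcomes, including the wound pain scale, at weeks 0, 6 and 12.

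| Outcome | Follow-up visits | Tests |
|---|---|---|
| Ulcer area | 3, 6, 9, 12 | 4 |
| Wound healed | visit not stated | 1 |
| PUSH | 3, 6, 9, 12 | 4 |
| SINBAD | 3, 6, 9, 12 | 4 |
| Pain | 6, 12 | 2 |
| EQ-5D-5L | 6, 12 | 2 |
| CWIQ | 6, 12 | 2 |

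Total: 4 + 1 + 4 + 4 + 2 + 2 + 2 = 19. Section 8.3 states the week-12 area test twice; it is counted once.

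- Low count: Table 2 has no pain row; without pain, 19 − 2 = 17.
- High count: pain and healed status both at all four visits, 19 + 2 + 3 = 24.

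**Step 2. Chance of at least one false significant result if Natrox has no effect.** Assumption: two-sided 0.05 per test.

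If the tests were independent: 1 − 0.95^19 = 0.62 (0.58 for 17 tests, 0.71 for 24). For a result favouring Natrox: 1 − 0.975^19 = 0.38.

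The tests are not independent. They are repeated measures on the same patients and the PUSH score includes ulcer size. The documents give no correlations, so a range is assumed. For 19 normal test statistics with equal pairwise correlation r:

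| r | Either direction, \|z\| > 1.96 | Favouring Natrox, z > 1.96 |
|---|---|---|
| 0.3 | 0.53 | 0.27 |
| 0.5 | 0.41 | 0.21 |
| 0.7 | 0.28 | 0.14 |
| 0.8 | 0.22 | 0.11 |

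**Step 3. Cross-check with the planned tests.** Trials with no effect were simulated with 12 per arm, 18 Mann-Whitney tests and one chi-squared test, an assumed 10% healed, and 4,000 trials per setting. The chance of any significant result was about 0.51 at correlation 0.5 within an outcome and 0.2 between outcomes, about 0.41 at 0.7 and 0.5, and about 0.24 at 0.9 and 0.8. The week-12 area test alone gave about 0.04 to 0.05.

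**Step 4. Would looking at week 12 only be enough?** Seven tests would remain (area, healed, five scores). In the model of step 2 they give 0.15 to 0.27 in either direction for r from 0.8 to 0.3, and 0.07 to 0.14 favouring Natrox. Limiting the visits helps, but several outcomes would still compete.

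**The case against.** Three objections have force.

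**Ranking.** A reader might infer that the plan has no hierarchy. The documents do not support that. Feasibility is primary and efficacy secondary; sections 5.6.2 and 6.1 put wound healing first among the clinical outcomes; section 8.3 makes week 12 the leading time point for area and places the scores under wider effects. What remains is that this ranking is never connected to the use made of the results in 8.2. Section 8.3 also makes the week-12 comparison depend on the size of the control group, without a threshold, so the leading test could be dropped while the others stay.

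**Size.** A reader might infer that a false significant result is likely. That needs near independence between tests. Under the assumed correlations the chance in either direction is mostly below one half, and a false result favouring Natrox stays at or below about 0.27.

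**Custom.** Adjustment for multiple secondary outcomes is not normally required in a feasibility trial, and the alpha level and multiplicity rules are commonly left to an SAP, which may exist. Section 8.2 sets no p-value rule either: it describes an overall judgement, and any larger trial would test efficacy again. All of this stands, so the absence of an alpha adjustment is not the fault. The fault lies in what the protocol itself states: significance tests without an exploratory label, beside a sentence allowing a final answer on effectiveness that is tied to none of them.

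**Conclusion.** The point holds in a limited form. The protocol fixes about 19 between-arm tests (17 to 24) and identifies a leading clinical measure, but does not confine effectiveness conclusions to it. For 19 tests, the chance of at least one false significant result is about 0.22 to 0.53 in either direction and about 0.11 to 0.27 in favour of Natrox, against a nominal 0.05 (0.025 in favour) for a single test. These figures rest on three assumptions: two-sided 0.05 per test, equal correlations between 0.3 and 0.8, and the visit count above. The conclusion does not depend on the exact values, since even the lowest is more than four times the single-test rate. This is a cheap improvement to what the pilot can claim; it does not undermine the feasibility objective.

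**What to change.** In section 8.3, state that the week-12 between-arm comparison of percentage change in ulcer area is the single efficacy contrast. Label all other outcomes and visits exploratory, reported as estimates with 95% confidence intervals and without significance claims. Reword the purpose of the healed-status analysis, now "to determine if there is a significant difference in distribution of treatment outcome in terms of 'status wound healed' (Natrox vs control", so that it estimates the difference between arms.

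In section 8.2, tie the signs of clinical effectiveness to that contrast. Delete the sentence allowing a final answer on effectiveness, or restrict it to the same contrast.

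No alpha adjustment is needed, and no change to data collection or sample size. The cost is a few sentences, and that a nominally significant secondary result can no longer be presented as a finding.

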Primary objective / outcome measures	To assess the feasibility of conducting a full RCT in the future - Participants' experience of and compliance with Natrox oxygen therapy - Recruitment and attrition rates, willingness of patients to consent and to be randomised, response rates to questionnaires, and degrees of missing data - Testing of eligibility criteria and ability/willingness of clinical staff to partake in recruitment and follow-up of participants - Adequacy of duration of follow-up (e.g. in relation to foot ulcer healing) - Appropriateness of inclusion/exclusion criteria and outcomes measures (both clinical and patient-reported). Descriptive assessment of wound size and characteristics (wk 0,3,6,9,12) Percentage 'wound healed' vs week 0 Percentage healing of the wound vs week 0 Change in semi-quantitative PUSH ulcer size score vs week 0 - SINBAD score (DFU only) vs week 0 - Wound closure status - Clinical characterisation of wound (erythema, purulence, odour, patient-reported pain) Safety of applied oxygen therapy in comparison to standard care arm (ongoing): - Wound infection incidence - Need for secondary interventions, such as surgery				
Secondary objectives / outcome measures					

	Patient-reported outcome measures (wk 0, 6, 12) - (Wound related) Quality of life scores (EQ-5D-5L and CWIQ) - Wound pain scale
Patient population	A total of 24 eligible participants will be randomised to receive either standard care or standard care plus Natrox topical oxygen therapy. Patients to be aged eighteen or over, with measurable foot ulcer present for at least two weeks, treated in podiatry clinic. Participants must have the capacity to provide informed written consent and complete patient reported outcome measures, and be willing and capable to wear the Natrox device.
	All participating patients – whose index wound has not healed by 50% or more in first four weeks of screening whilst in the study and under care of podiatry team - will be randomised for the trial phase. Those patients who were enrolled and whose foot ulcer healed 50% or more complete the study at the end of the four-week screening phase.
	In summary, of those participants whose wound does not heal 50% in four-week screening phase: - 12 Patient will receive treatment as usual (TaU) - 12 Patients will receive TaU plus adjunct Natrox topical oxygen therapy
	Randomisation will be stratified for ulcer size, with cut-off PUSH score of up to and including 5, and 6 and above.

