6.1.1 Randomisation

Following written consent at -4 weeks, participants will be observed for four weeks to establish healing rate. At the end of four weeks, patients are only eligible for the intervention phase if their wound has healed <50% in the preceding four weeks. At this point, week 0, participants are allocated at random to the control or Natrox intervention group, using a randomised sequence from the freeware randomisation programme, see https://www.randomizer.org/. The randomisation is stratified for ulcer size, with PUSH score of 5 or less, and 6 or above as the cut-off. This size has been determined as the average size of a presenting foot ulcer previously (Zimny et al, 2002).

Sequential envelopes with each next randomisation allocation will be used to achieve concealment and these will be kept in the research department. The researcher will then inform the regular healthcare professional for the participant in question, and the participant themselves, which treatment they've been allocated to. The researcher will dispatch a Natrox device to the clinic where the participant will be seen. At this stage the continuous Natrox treatment (though disconnection for washing or changing of clothes is allowed) will commence.

As the study involves administration of a visible device, it is not possible to achieve blinding for the participants nor the researchers – it is recognised that this increases the risk of bias. Since the device has an indicator to show it is functioning, applying a sham device is not possible either on this occasion.

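### Section 8.3 tests five secondary scores on unadjusted change from week 0; this is valid, but adjusting for the week-0 score already collected would add precision at almost no cost

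*Protocol*

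**What the plan says.** Section 8.3 treats five scores separately from ulcer area: PUSH, SINBAD, a visual analogue pain score, EQ-5D-5L and CWIQ. For these, "the following parameters will be compared (median difference between week 0 and different follow-up time points"). The test and its reason follow: "To compare, Mann-Whitney U-test between cohorts, since data is ordinal". No covariate is mentioned.

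The week-0 values have two uses: they are subtracted from the follow-up value, and they describe the arms at baseline. The list of baseline variables to be described and compared includes "baseline wound size (cm2), PUSH score, SINBAD DFU grading score (if applicable), EQ5-5D-5L score, CWIQ score".

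Collection at week 0 is planned. Table 2 has week-0 entries for PUSH, SINBAD (diabetic foot ulcers only), CWIQ and EQ-5D-5L, and section 5.6.2 lists "Patient-reported outcome measures (wk 0, 6, 12"). Pain is less certain. The protocol summary puts "Wound pain scale" under the patient-reported measures and also mentions patient-reported pain as part of wound characterisation. Table 2 has no row for a pain score, and section 5.6.2 does not list one.

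PUSH also defines the strata: "The randomisation is stratified for ulcer size, with PUSH score of 5 or less, and 6 or above as the cut-off" (section 6.1.1). Section 8.2 names "positive changes in foot ulcer related quality of life" among the considerations for a larger trial.

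**The concern.** Two features of the rule invite a second look.

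The first is scale. A Mann-Whitney test needs only an ordering, so it suits an ordinal score. Here it is applied to differences of scores, and a difference has a meaning across patients only if one step is worth the same everywhere on the scale. Ranking afterwards does not remove that assumption. How far a score can fall also depends on where it starts, and the trial takes patients on both sides of the PUSH cut-off.

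The second is precision. Subtracting the week-0 score fixes its coefficient at 1, whatever the correlation between visits. When the correlation is modest, this adds week-0 noise to the outcome. Using the week-0 score as a covariate lets the data set the coefficient.

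At stake is the precision of secondary comparisons in a 24-patient trial, some of which feed the judgement on a larger study.

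**Working it through.** **Inputs.** From the protocol: 12 per arm, 24 in total (section 6.1); change from week 0; Mann-Whitney; no covariate (section 8.3). Not given, so assumed: effect size (1 SD, with 0.8 SD as a check), rho from 0.3 to 0.9, ratio k of follow-up SD to week-0 SD (1 or 1.5), two-sided alpha of 5%.

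**The plan's own figure.** 12 + 12 = 24 agrees. The number comes from a rule of thumb for pilot studies, so there is no power calculation to reproduce.

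**Scale check.** Take two patients, one going from 2 to 0 and one from 8 to 5. Their changes are -2 and -3, so the second improves more. Recode the score by its square root, which keeps every ordering. The changes become 0 - 1.41 = -1.41 and 2.24 - 2.83 = -0.59, so the first now improves more. The ranks of changes are not protected by the ordinal property.

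**Variance.** In units of the week-0 variance:

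- change: 1 + k² - 2·rho·k
- adjusted for week 0: k²(1 - rho²)
- change minus adjusted: (1 - rho·k)², which is never negative

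Apart from the small cost of estimating the slope, adjustment therefore cannot lose. It gains nothing where rho·k = 1. With k = 1 the ratio of adjusted to change reduces to (1 + rho)/2.

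| k | rho | change | adjusted | ratio |
|---|---|---|---|---|
| 1 | 0.3 | 1.40 | 0.91 | 0.65 |
| 1 | 0.5 | 1.00 | 0.75 | 0.75 |
| 1 | 0.7 | 0.60 | 0.51 | 0.85 |
| 1 | 0.9 | 0.20 | 0.19 | 0.95 |
| 1.5 | 0.3 | 2.35 | 2.05 | 0.87 |
| 1.5 | 0.5 | 1.75 | 1.69 | 0.96 |
| 1.5 | 0.7 | 1.15 | 1.15 | 0.998 |

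Estimating the slope in 24 patients multiplies the adjusted variance by about 1 + 1/(24 - 4) = 1.05. This takes the k = 1 ratios to 0.68, 0.79, 0.89 and 1.00.

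**Simulated power, 12 per arm, 1-SD effect, integer scores.** Mann-Whitney on change against rank analysis of covariance:

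| rho | k = 1 | k = 1.5 |
|---|---|---|
| 0.3 | 46% v 65% | 60% v 65% |
| 0.5 | 60% v 71% | 71% v 73% |
| 0.7 | 81% v 83% | 88% v 85% |

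A separate run with k = 1.5 on a 0-17 score gave 58% v 64%, 72% v 71% and 87% v 84%. Ordinary analysis of covariance was at least as powerful as Mann-Whitney on change in every case.

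**Smaller effect.** For 0.8 SD with k = 1 on a 0-17 score (8,000 runs per case), power was 32% v 46%, 40% v 52%, 62% v 68% and 96% v 95% at rho 0.3, 0.5, 0.7 and 0.9. On a 0-6 score it was 30% v 46%, 38% v 50%, 55% v 63% and 88% v 89%. With 10 per arm, rho 0.5 and the 0-17 score, it was 34% v 45%.

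**No effect.** Rejection rates in the same 8,000-run simulations at 12 per arm were 4.3% to 4.9% for Mann-Whitney on change and 4.7% to 5.2% for the rank analysis.

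**The case against.** The best defence is that the planned test is valid, familiar and fixed in advance, and that the outcomes are secondary in a feasibility trial with no power target. All of that stands.

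Three stronger readings are tempting but not supported.

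- **The stated reason contradicts the method.** In context, the remark about ordinal data explains why these scores go straight to Mann-Whitney, whereas ulcer area may go to a t-test if normally distributed. It is a reason for the test, not for taking differences. The spacing assumption is real, but it is a common simplification for summed scores and not a clash of two instructions. Stratifying on PUSH also helps to balance starting PUSH between arms.
- **The planned test is clearly weaker, so that 24 patients do the work of about 16.** That figure is 24 × 0.65 = 15.6, and it needs both rho 0.3 and equal variances. Unequal variances are plausible for the wound scores, because entry requires less than 50% healing during screening while follow-up can run from healed to deteriorated. With k = 1.5 the same calculation gives 24 × 0.87 = 20.9 at rho 0.3 and 24 × 0.96 = 23.0 at rho 0.5.
- **The go/no-go decision hangs on these tests.** Section 8.2 lists quality of life beside several feasibility inputs and sets no significance rule. Its remark about a possible definitive answer concerns clinical effectiveness, for which section 8.3 uses ulcer area as the main measure.

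A further objection concerns the remedy. The rank analysis gives a p-value but no interval on the score scale, so it should not be the main analysis. This is accepted in the fix.

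**Conclusion.** The point holds as an efficiency improvement to secondary outcomes. It is not an error in a stated figure, a bias or an invalid test. Section 8.3 itself fixes the unadjusted change comparison, so this is not a detail merely left to a later analysis plan.

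The size depends on rho and k, neither of which the protocol gives. With equal variances and a 1-SD effect, the rank analysis gains about 19, 11 and 2 points of power at rho 0.3, 0.5 and 0.7. With a follow-up SD 1.5 times the week-0 SD, it gains about 5 and 2 points at rho 0.3 and 0.5 and loses about 3 at rho 0.7. Nobody can know beforehand which case applies. Ordinary analysis of covariance did at least as well as the planned test throughout, so choosing it carries little risk. The simulations assume scores that are rounded normal, full follow-up and a shift of location. SINBAD is scored only in diabetic foot ulcers, so its comparison will rest on fewer than 24 patients if other aetiologies are enrolled.

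**What to change.** In section 8.3, replace the rule for the five scores with this:

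- For each score, compare the follow-up value between arms by analysis of covariance with the week-0 score as covariate. Report the adjusted difference with its 95% confidence interval at week 12.
- Name one rank-based sensitivity test in advance, rank analysis of covariance, reported as a p-value only.
- Analyse SINBAD in participants with diabetic foot ulcers only.
- Analyse pain in this way only if a week-0 value is collected, and reconcile Table 2 and section 5.6.2 with the summary on this.
- Show median change per arm as description, and drop the ordinal-data remark as the ground for the comparison.

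The cost is a wording change. It needs no new visits or patients, and no new data beyond settling whether pain is scored at week 0. The downside is one covariate per model in a small sample, and reliance on an approximately linear model for short scales, which the rank-based sensitivity test is there to check.
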